5.5.9 Exposure to light

Patients need to be advised to limit exposure to UV light (including sunbathing and/or use of UV tanning devices) during the study to avoid possible effect on psoriasis.

5.5.10 Discontinuation of study drug

Patients may voluntarily discontinue study drug for any reason at any time.

The Investigator/qualified site staff should discontinue study drug for a given patient if, on balance, he/she believes that continuation would be detrimental to the patient's well-being.

If discontinuation occurs for any reason in a treatment period, the Investigator/qualified site staff must make every effort to determine the primary reason for a patient's discontinuation from the study drug. This information will then be recorded in the eCRF.

Study drug *must* be discontinued under the following circumstances:

- Emergence of the following AEs: AEs that in the judgment of the Investigator/qualified site staff, taking into account the patient's overall status, prevent the patient from continuing study drug (for example, sepsis or serious infection).
- Any laboratory abnormalities that in the judgment of the Investigator/qualified site staff
 taking into consideration the patient's overall status, prevents the patient from continuing
 study drug.
- Pregnancy (see Section 6.5.6 and Section 7.4).

[‡] In case of undue safety risk for the patient, the patient should discontinue study drug at the discretion of the Investigator/qualified site staff. If the patient received a live virus vaccination during the study, the patient must discontinue study drug.

[§] Inhalative CS with only a topical effect (eg, to treat asthma) are not considered "**systemic** immunomodulating treatments" and are therefore acceptable as comedication.

^{*} Mild to moderate TCS used on the face, scalp and/or genitoanal area must be stopped at the latest on the day prior to the Baseline Visit (Day 1).

^{**} No TCS is allowed during Treatment Period 1 (from Baseline Visit [Day 1] to Week 24 visit pre-dose).

• Use of prohibited treatment as per recommendations in Section 5.5.8.

Patients discontinued from study drug will NOT be considered discontinued from the study. The Investigator/qualified site staff must record the date and primary reason for stopping the study drug.

At the time of the study drug discontinuation visit, IF it has been at least 4 weeks after the last dose of study drug, THEN the assessments described for the end of treatment period 1 (EOT1) visit/Week 24 (for early discontinuation during **Treatment Period 1**) or the end of treatment period 2 (EOT2) visit/Week 52 (for early discontinuation during **Treatment Period 2**) should be completed at this visit. The patient will then return per appropriate schedule for visit Week 60, if applicable.

IF it has not been at least 4 weeks after the last dose of study drug at the time of the study drug discontinuation visit, THEN the patient should be scheduled to return 4 weeks post last dose for their EOT1 visit (Week 24) or EOT2 visit (Week 52) assessments, respectively. The patient will then return per appropriate schedule for the Week 60 visit, if applicable.

The Investigator/qualified site staff must contact the IRT when the patient completes the EOT1 visit (Week 24) or EOT2 visit (Week 52) assessments to register the patient's early completion of the study due to study drug discontinuation. See Section 6 for the required assessments of these patients after study drug discontinuation.

5.5.11 Discontinuation from a treatment-free period

If discontinuation occurs for any reason in the treatment-free follow-up period, the Investigator/qualified site staff must make every effort to determine the primary reason for a patient's premature withdrawal from the study. This information will then be recorded by Investigator/qualified site staff on the applicable section of the eCRF.

See Section 6 for the required assessments of those patients who discontinue from the follow-up period.

5.5.12 Withdrawal of consent

Patients may voluntarily withdraw consent to participate in the study for any reason at any time.

Withdrawal of consent occurs only when a patient does not want to participate in the study anymore and does not want any further visits or assessments and does not want any further study related contacts and does not allow analysis of already obtained biologic material.

If a patient withdraws consent, the Investigator must make every effort (eg, telephone, e-mail, letter) to determine the primary reason for this decision and record this information. The study drug must be discontinued and no further assessments or follow-up visits conducted. All biological material that has not been analyzed at the time of withdrawal must not be used. Further attempts to contact the patient are not allowed unless safety findings require communicating or follow up.

5.5.13 Loss to follow-up

For patients whose status is unclear because they fail to appear for study visits without stating an intention to withdraw, the Investigator should show "due diligence" by contacting the

patient, family or family physician as agreed in the informed consent and by documenting in the source documents steps taken to contact the patient, eg dates of telephone calls, registered letters, etc. A patient should not be considered lost to follow-up until his/her scheduled end of study visit would have occurred.

5.5.14 Emergency breaking of assigned treatment code

Not applicable.

5.5.15 Study completion and post-study drug

Study completion is defined as all patients who have been enrolled and completed the study as per the protocol.

The Investigator must provide follow-up medical care for all patients who are prematurely withdrawn from the study, or must refer them for appropriate ongoing care.

If there is the possibility that patients can participate in an extension study the eligibility criteria and all study details should be explained in a corresponding study protocol.

5.5.16 Early study termination

The study can be terminated at any time for any reason by Novartis. Should this be necessary, the patient should be seen as soon as possible and treated as a discontinued patient as described in Section 5.5.10. The Investigator may be informed of additional procedures to be followed in order to ensure that adequate consideration is given to the protection of the patient's interests. The Investigator will be responsible for informing the Institutional Review Board/Independent Ethics Committee (IRB/IEC) of the early termination of the study.

6 Visit schedule and assessments

Table 6-1 lists all of the assessments and indicates with an "X" when the visits are performed. An 'S' indicates the data for that assessment are in the source documents at the site. Patients should be seen for all visits on the designated day or as closely as possible to the original planned visit schedule (recommended visit windows are in Table 6-1). Every effort should be made to respect the timeframe for all visits.

If for any reason the patient is a screen failure, the patient may be rescreened. If the reason for screen failure is regarded as a transient constraint for study participation then there is no restriction on the number of times a potential patient may be rescreened or on how much time must pass from the date of screen failure and the date of rescreening.

IF a patient rescreens for the study, THEN the patient must sign a new ICF and be issued a new Patient Number prior to any Screening assessment being conducted for the patient under the new Screening Patient Number. For all patients, the Investigator/qualified site staff will record if the patient was rescreened on the eCRF and any applicable Screening numbers the patient was issued prior to the current Screening number.

The date of the new informed consent signature must be entered on the eCRF to correspond to the new Screening Patient Number. Informed consent for a rescreened patient must be obtained prior to performing any study-related assessment or collecting any data for the Screening Visit. For rescreening, all Screening assessments must be performed in accordance

with the protocol, except for the chest X-ray or TB work-up, if applicable, if performed not more than 12 weeks prior to Day 1 (Baseline). If patients do not have a chest X-ray available within 12 weeks of the projected Day 1 date, the X-ray should be performed after it is certain the patient meets inclusion/exclusion criteria in order to minimize unnecessary exposure to radiation.

If the date of the TB work-up is less than 12 weeks from Baseline then the TB work-up does not have to be repeated; however, the patient must repeat the QFT performed by the central laboratory.

During the Treatment Periods 1 and 2, patients may be seen at an unscheduled visit, eg, if they experience deterioration of psoriasis or suspected AEs. During these unscheduled visits, study drug will NOT be administered.

Recommended visit windows

Treatment periods:

- ± 2 days for Baseline, Week 1, Week 2, Week 3 and Week 4 and for Week 24.
- ± 2 days for all study drug home administrations.
- \pm 5 days for all other study visits.
- Visit 1 and Visit 2 must not be conducted at the same day and all relevant information for Visit 2 must be available before treating the patient. The screening period might not be longer than 4 weeks.

For patients who discontinue study drug prematurely before the end of the Treatment Period 1 for any reason other than withdrawal of informed consent, the Week 24 (planned EOT1) visit must be performed at least 28 days (4 weeks) after the last drug administration and the patient should then enter the treatment free follow-up period, if applicable.

For patients who discontinue study drug prematurely before the end of the Treatment Period 2 for any reason other than withdrawal of informed consent, the Week 52 (planned EOT2) visit must be performed at least 28 days (4 weeks) after the last drug administration and the patient should then enter the treatment free follow-up period, if applicable.

If a patient refuses to return for these assessments or is unable to do so, every effort should be made to contact them, or a knowledgeable informant, by telephone or by sending appropriate correspondence (ie, certified letter) immediately. At this contact, the safety (eg, potential occurrence of AEs or SAEs) and the primary reason for the patient's premature withdrawal should be determined. Documentation of attempts to contact the patient should be recorded in the patient source documents.

For Group 3 and Group 4 at a minimum, patients will be contacted for safety evaluations during the 12 weeks following the last dose of study drug, including final contact at the 12-week point or the 30 days point following the last study visit (whichever is later). Documentation of attempts to contact the patient should be recorded in the patient's record.

Recommended order of assessments:

The recommended order of PRO assessment for completion by the patient is as follows:

- DLOI
- Patient's assessment of pain, itching and scaling

- EQ-5D[©] Health Status Questionnaire
- WPAI-PSO

The recommended order of efficacy and other assessments, which will be completed by the Investigator/qualified site staff, is as follows:

- IGA mod 2011 assessments (performed by the blinded assessor)
- PASI assessments (performed by the blinded assessor)
- Review PRO data (at applicable visits).
- Physical examination (at applicable visits).
- All remaining study visit procedures (eg vital signs measurements) are to be completed prior to study drug dosing
- Safety blood samples and PK blood sample will be collected
- Contact IRT to register the patient visit and enter all data as applicable.
- Self-administration of study medication. Note: if needed, a caregiver of the patient can be trained for home administration to provide support to the patient; corresponding training should be documented in the source data at the study center (see Section 5.5.4).

Table 6-1 Assessment schedule

Period	Scr		Treatment Period 1									Treatment Period 2								ita	Comments
Visit	1	2	3	4	5	6	7	8	9	10	11	12	13	14	15	16	17	18	19	d Vis	
Week	-4 to BL ^e	BL	1	2	3	4	8	12	16	20	24 a, b	28	32	36	40	44	48	52 c	60	Unscheduled Visit ^d	
Recommended visit window (days)			±2	±2	±2	±2	±5	±5	±5	±5	±2	±5	±5	±5	±5	±5	±5	±5	±5	Uns	
Informed consent	Χ																				
Demographics	Χ																				
Inclusion/exclusion criteria	X	x																			These assessments are supported by and stored within the source documentation. Data relating to inclusion/exclusion criteria are captured in the corresponding eCRF.
Smoking history	Χ																				
Psoriasis: medical history / previous psoriasis therapies	Х																				
Other medical history and prior medications	Х																				
Concomitant medications	Х	Х	Х	Х	Х	Х	Х	Х	Х	Х	Х	Х	Х	Х	Х	Х	Х	Х	Х	Х	
Physical examination	S	S	S	S	S	S	S	S	S	S	S	S	S	S	S	S	S	S	S	S	
Height	Χ																			X	
Weight	Χ	Χ									Χ							Х	Х	Χ	
Vital signs	Χ	Х				Χ		Χ	Χ		Х	Χ		Χ			Χ	Х	Х	X	
Laboratory sampling: safety panel (Clinical chemistry including urine, hematology)	X	х				×		x	х		х	х		х			х	х	х	х	For processing of samples please refer to the manual of the central lab.

Period	Scr				Tre	atmen	t Perio	d 1						Treati	ment P	eriod 2	2		FU	it ^d	Comments
Visit	1	2	3	4	5	6	7	8	9	10	11	12	13	14	15	16	17	18	19	d Vis	
Week	-4 to BL °	BL	1	2	3	4	8	12	16	20	24 a, b	28	32	36	40	44	48	52 c	60	Unscheduled Visit ^d	
Recommended visit window (days)			±2	±2	±2	±2	±5	±5	±5	±5	±2	±5	±5	±5	±5	±5	±5	±5	±5	Nus	
Chest X-ray (or CT/MRI)	S																			S	Where a patient has not had a chest X-ray, chest CT or chest MRI, CT performed within 3 months prior to Screening, an image should be obtained once it is clear that the patient meets the other inclusion/exclusion criteria in order to minimize unnecessary exposure X-ray radiation.
QuantiFERON® TB-Gold In-tube test ^e	Х																			Х	see lab manual
Serum pregnancy test	Х																			Х	Only for females of child- bearing potential.
Urine pregnancy test (local)		x				x		x	x		х			x				x	x	х	In the event of a positive urine pregnancy test, study drug must be withheld and a serum pregnancy test performed at the same visit. A urine pregnancy test is not required for a woman who is sterile or who is postmenopausal.
ECG (standard 12-lead)		Х									Х							Х	Х	Х	
PASI	Х	Х	Х	Х	Х	Х	Х	Х	Х	Х	Х	Х	Х	Х	Х	Х	Х	Х	Χ	Х	
BSA	Х	Х																Х		Х	

Period	Scr				Tre	atmen	t Perio	d 1				Treatment Period 2								ita	Comments
Visit	1	2	3	4	5	6	7	8	9	10	11	12	13	14	15	16	17	18	19	d Vis	
Week	-4 to BL ^e	BL	1	2	3	4	8	12	16	20	24 a, b	28	32	36	40	44	48	52 c	60	Unscheduled Visit ^d	
Recommended visit window (days)			±2	±2	±2	±2	±5	±5	±5	±5	±2	±5	±5	±5	±5	±5	±5	±5	±5	Uns	
IGA mod 2011	Χ	Χ	Χ	Χ	Χ	Х	Χ	Х	Χ	Χ	Χ	Χ	Χ	Χ	Χ	Х	Χ	Х	Χ	Х	
DLQI		Х				Χ		Χ			Χ			Х			Χ	Х		Х	
WPAI-PSO		Х				Х		Χ			Χ			Χ			Χ	Χ		Х	
Assessment of pain, itching and scaling		Х				Х		Х			Х			Х			Х	Х		Х	
EQ-5D [©]		Х				Х		Х			Х			Х			Χ	Х		Х	
AE assessment (including injection site reactions)	х	х	х	х	х	Х	х	Х	Х	х	Х	х	х	х	х	Х	Х	Х	х	х	
Assessment of rebound																			x		Unscheduled rebound assessment only to be done at an unscheduled visit that occurs during the post-treatment follow-up period.
Randomization by IRT											Х										
IRT contact such as for registration or drug supply including home administration	х	х	х	х	х	x	х	x	х	x	х	х	x	х	x	x	x	х			
PK blood sample		x						x			х			х			×			x	Samples will be shipped by the sites and stored by the central laboratory. Samples will be shipped to reference laboratories for analysis. Samples need to be taken before dosing.

Page 49

Period	Scr				Tre	atmen	t Perio	d 1					Treatment Period 2						FU	it	Comments
Visit	1	2	3	4	5	6	7	8	9	10	11	12	13	14	15	16	17	18	19	d Visit ^d	
Week	-4 to BL ^e	BL	1	2	3	4	8	12	16	20	24 a, b	28	32	36	40	44	48	52 c	60	cheduled	
Recommended visit window (days)			±2	±2	±2	±2	±5	±5	±5	±5	±2	±5	±5	±5	±5	±5	±5	±5	±5	Uns	
Check self- administration log												S	S	s	S	S	S	S		S	Patients must return the self-administration log along with all dispensed PFS and drug packaging at every visit, if applicable.
Complete Screening period eCRF	Х																				
Complete end of Treatment Period 1 eCRF											х										
Complete end of Treatment Period 2 eCRF																		Х			

Footnotes:

- a Visit 11, patients will have the last assessment for Treatment Period 1 performed prior to administration of study drug.
- b Visit 11 assessments must be completed for patients who discontinue study drug prematurely during Treatment Period 1; patient should then enter the post treatment follow-up period, if applicable.
- c Visit 18 assessments must be completed for patients who discontinue treatment prematurely during Treatment Period 2.
- d Unscheduled visit assessments at discretion of the Investigator.
- e A repeat QuantiFERON® TB-Gold In-Tube test is recommended if the result of the first QuantiFERON® TB-Gold In-Tube test is "indeterminate". The patient must be referred for a follow-up TB work-up (as per local guidelines) if either the first or the repeat test is "positive" or if the results of both tests are "indeterminate". If the first test is indeterminate, the Investigator may decide not to repeat the test and to proceed directly to the work-up, though this is not recommended. The patient will not be eligible for enrollment if "active TB is present "or if "latent TB is present" and is untreated as per local guidelines.

Abbreviations:

AE: adverse event; BL: baseline; CT: computer tomography; DLQI: Dermatology Life Quality Index; ECG: electrocardiogram; eCRF: electronic case report form; EOT: end of treatment; EQ-5D[©]: EuroQOL 5-Dimension Health Questionnaire; FU: follow-up; IGA: Investigator's Global Assessment; IRT: interactive response technology; MRI: magnetic resonance imaging; PASI: Psoriasis Area and Severity Index; PFS: pre-filled syringe; PK: pharmacokinetic; S = assessment to be recorded on source documentation Scr: screening; TB: tuberculosis; Uns: unscheduled visit; WPAI-PSO: Work Productivity and Activity Impairment Questionnaire-Psoriasis; X = assessment to be recorded on clinical database

Table 6-2 Overview of study drug administration for Treatment Period 2

Visit	11		12		13		14		15		16		17	18
Week	24	26	28	30	32	34	36	38	40	42	44	46	48	52
Recommended visit window (days)	±2	±2	±5	±2	±5	±2	±5	±2	±5	±2	±5	±2	±5	±5
Study drug administration														
Group 1	S		S		S		S		S		S		S	
Group 2	S			Н			S			Н			S	
Group 3	S		S		S		S		S		S		S	
Group 4	S	Н	S	Н	S	Н	S	Н	S	Н	S	Н	S	

Abbreviations: H = home administration; S = administration at study center

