IRT Interactive Response Technology

L Lower limbs [PASI scoring system]

LFT Liver Function Test

MedDRA Medical Dictionary for Regulatory Activities

NR Non Responder

NRS Numeric Rating Scale

NYHA New York Heart Association

PASI Psoriasis Area and Severity Index

PFS Pre-Filled Syringe PR Partial Responder

PRO Patient Reported Outcomes

RAN Retreatment as Needed Serious Adverse Event SAE

s.c. Subcutaneous, subcutaneously

Serum Glutamic Oxaloacetic Transaminase **SGOT**

SGPT Serum Glutamic Pyruvic Transaminase

SOC System Organ Class

SUSAR Suspected Unexpected Serious Adverse Reaction

T Trunk [PASI scoring system]

TB **Tuberculosis**

TCS Topical Corticosteroid TNF Tumor Necrosis Factor

U Upper limbs [PASI scoring system]

UNL Upper Normal Limit

UV Ultraviolet

White Blood Cells **WBC**

WPAI-PSO Work Productivity and Activity Impairment Questionnaire-Psoriasis

Glossary of terms

Assessment	A procedure used to generate data required by the study.	
Enrollment	Point/time of patient entry into the study at which informed consent must be obtained prior to starting any of the procedures described in the protocol.	
Medication number	A unique identifier on the label of each study drug package in studies that dispense medication using an Interactive Response Technology (IRT) system.	
Protocol	A written account of all the procedures to be followed in a study, which describes all the administrative, documentation, analytical and clinical processes used in the study.	
Premature patient withdrawal	Point/time when the patient exits from the study prior to the planned completion of all study drug administration and/or assessments; at this time all study drug administration is discontinued and no further assessments are planned, unless the patient is followed for progression and/or survival.	
Randomization number	A unique identifier assigned to each randomized patient, corresponding to a specific treatment group assignment.	
Study drug	Any single drug or combination of drugs administered to the patient as part of the required study procedures; includes investigational drug(s), active drug run-ins, or background therapy.	
Patient number	A number assigned to each patient who enrolls into the study.	
Variable	A measured value or assessed response that is determined in specific assessments and used in data analysis to evaluate the drug being tested in the study.	

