From the standpoint of the overall risk-benefit assessment, the current study with secukinumab is justified.

4 Population

The study population will consist of a representative group of male and female patients (\geq 18 years old) with moderate to severe chronic plaque psoriasis and candidates for systemic treatment. Moderate to severe chronic plaque psoriasis is defined by a total PASI score of \geq 10 and a body surface area (BSA) of \geq 10% approaching a described European consensus (Mrowietz et al 2011).

It is planned that approximately 2257 patients will be screened and around 1580 patients will be enrolled at Baseline to randomize 570 patients at Week 24 each for Group 1 and Group 2 (relevant groups for primary objective). Sample size details are provided in Section 9.7. Patients who drop out after they have been randomized will not be replaced. If a patient fails to be enrolled at Baseline, the patient may be rescreened if it can be assumed that the cause of Screening failure is only a temporary constraint. Patients may be screened more than once.

Randomization will be stratified by body weight at Week 24 (randomization visit). The strata will be "body weight $\geq 90 \text{ kg}$ " or "body weight $\leq 90 \text{ kg}$ " for all treatment groups.

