- 15. Total white blood cell (WBC) count $< 2500/\mu$ L, platelets $< 100~000/\mu$ L, neutrophils $< 1500/\mu$ L or hemoglobin < 8.5~g/dL, at Screening.
- 16. Active systemic infections during the 2 weeks prior to Baseline (exception: common cold) or any infection that reoccurs on a regular basis.
- 17. History of an ongoing, chronic or recurrent infectious disease, or evidence of tuberculosis (TB) infection as defined by a positive QuantiFERON TB-Gold test (QFT) at Screening. Patients with a positive or indeterminate QFT test may participate in the study if full TB work-up (according to local practice/guidelines) completed within 12 weeks prior to Day 1 (Baseline) establishes conclusively that the patient has no evidence of active TB. If presence of latent TB is established, then treatment must have been initiated and maintained according to local country guidelines prior to Day 1 (Baseline).
- 18. Chest X-ray, computerized tomography (CT) scan, or MRI with evidence of ongoing infectious or malignant process, obtained within 12 weeks prior to Baseline, and evaluated by a qualified physician.
- 19. Past medical history record of, or current infection with, human immunodeficiency virus (HIV), hepatitis B virus or hepatitis C virus prior to Baseline.
- 20. History of lymphoproliferative disease or any known malignancy or history of malignancy of any organ system within the past 5 years (except for skin Bowen's disease, or basal cell carcinoma or actinic keratoses that have been treated with no evidence of recurrence in the past 12 weeks; carcinoma *in situ* of the cervix or non-invasive malignant colon polyps that have been removed).

- 21. Current severe progressive or uncontrolled disease which in the judgment of the Investigator renders the patient unsuitable for the study or puts the patient at increased risk (eg, myocardial infarction within 26 weeks prior to Baseline).
- 22. Inability or unwillingness to undergo repeated venipuncture (eg, because of poor tolerability or lack of access to veins).
- 23. Any medical or psychiatric condition which, in the Investigator's opinion, would preclude the patient from adhering to the protocol or completing the study per protocol.
- 24. History or evidence of ongoing alcohol or drug abuse, within the last 6 months prior to Baseline.
- 25. Plans for administration of live vaccines during the study period or in the 6 weeks prior to Baseline.

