6.2.5.1 Chest X-Ray

A chest X-ray, CT scan, or MRI obtained within 12 weeks prior to enrollment will be used to determine eligibility. If patients do not have a chest X-ray, CT scan, MRI available within 12 weeks prior to enrollment, a chest X-ray (or chest MRI at pre-specified sites) only must be done after it is fairly certain the patient meets the other inclusion/exclusion criteria in order to minimize unnecessary exposure to X-ray radiation for patients.

If the chest X-ray, CT scan, or MRI evaluated by a qualified physician shows evidence of ongoing infection or malignancy and the patient was not treated subsequent to the X-ray (CT scan or MRI), the patient will not be eligible to enter the study.

Prior and concomitant medications 6.2.6

Concomitant medications and prior medications taken over the 6 months preceding the study Screening Visit (Visit 1) will be captured in the eCRF and any other relevant medication taken before 6 months at the discretion of the Investigator.

6.2.7 **Determination of tuberculosis status**

Determination of TB status will be required before administration of study drug and should be performed as defined by local guidelines. TB status must be determined by medical history, signs, symptoms, and TB testing (QuantiFERON-TB Gold assay).

Any significant findings will be recorded in the TB Assessment eCRF and the Medical History eCRF, as necessary.

A QuantiFERON® TB-Gold In-Tube assay will be performed to assess the TB status at Screening for all patients. This test will only be used to determine patient's eligibility for the study. The test will be used to screen the patient population for latent TB infection (Doherty et al 2008). This blood-based assay is specific for *Mycobacterium tuberculosis* and is not influenced by previous Bacillus Calmette-Guérin vaccination or exposure to other Mycobacteria species. This test, in contrast to the purified protein derivative skin test, is also insensitive to a booster effect since the patient is not exposed to the vaccine. The assay measures the production of interferon-gamma and presents it relative to a negative and a positive control sample (Manuel and Kumar 2008). The QuantiFERON®-TB Gold assay test will be supplied by the central laboratory. Details on the collection, shipment of samples and reporting of results by the central laboratory are provided to Investigators in the laboratory manual.

- If the test result is negative, the patient may be enrolled.

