#### 1.4.3 Screening, baseline and post-baseline definitions

Screening refers to any procedures (e.g., checking inclusion and exclusion criteria) performed prior to the date of visit 2. Per protocol, subject informed consent must be obtained prior to performing any study related activity. The date of signing informed consent is the start date of screening period. Any assessment obtained during the screening period will be labeled screening assessment.

Visit 2 is defined as *Baseline* visit. All consecutive visits are labeled according to the preplanned study week where they occur, i.e. Week 1, Week 2, and so on.

Week 24 is defined as the end of Treatment Period 1 (visit 11) for patients without premature discontinuation during Treatment Period 1. For patients with premature termination within Treatment Period 1 the last visit is defined as end of Treatment Period 1.

Week 52 is defined as the end of Treatment Period 2 (visit 18) for patients without premature discontinuation during Treatment Period 2. For patients with premature termination in Treatment Period 2 the last visit is defined as end of Treatment Period 2.

Any visits and assessments occurring after the end of Treatment Period 2 visit (Week 52 in the eCRF) will be aligned to the Week 60 Follow-Up visit.

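### The Table 6-1 chest-imaging comment looks back 3 months from Screening, further than the 12 weeks before Baseline set by exclusion criterion 18

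*Protocol*

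**What the plan says.** The protocol sets the look-back for chest imaging in several places.

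- **Section 4.2, criterion 18** (repeated in the synopsis) excludes a patient whose chest X-ray, CT or MRI comes back "with evidence of ongoing infectious or malignant process, obtained within 12 weeks prior to Baseline".
- **Section 5.5.1 and the opening text of Section 6**, on rescreening, exempt the chest X-ray from repetition on the same 12-week count back from Baseline. Section 6 adds that an X-ray should be done if the patient has none within 12 weeks of the projected Day 1.
- **Section 6.2.5.1** says an image "obtained within 12 weeks prior to enrollment will be used to determine eligibility", and requires an X-ray (or MRI at certain sites) where none is available in that window.
- **Table 6-1, chest X-ray row**, carries a comment about patients who have had no chest imaging "performed within 3 months prior to Screening, an image should be obtained once it is clear" that the other criteria are met.

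The length of screening is set by two statements in Section 6: "Visit 1 and Visit 2 must not be conducted at the same day" and "The screening period might not be longer than 4 weeks". SAP 1.4.3 fixes where that period begins: "The date of signing informed consent is the start date of screening period".

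**The concern.** The Table 6-1 comment differs from the other texts in both length and anchor. It uses 3 months instead of 12 weeks, and it counts from Screening instead of Baseline. Both differences lengthen the window, and they add together.

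The image is there to detect infection or malignancy before the first dose of an immunomodulating biologic. Site staff are likely to plan visits from the assessment schedule, and that is where the longest window stands. A patient could meet the table's condition and be dosed with no image recent enough for criterion 18. Read literally, criterion 18 would not catch this by itself, because it excludes on an abnormal recent image and does not mention a missing one.

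**Working it through.** **Inputs**

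- Criterion 18: 12 weeks = 12 × 7 = 84 days before Baseline (Day 1). This is the plan's own limit.
- Table 6-1 comment: 3 calendar months before Screening. The shortest such span is 28 + 31 + 30 = 89 days (February to April, non-leap year). The longest is 92 days, for example 30 + 31 + 31 (June to August).
- Screening to Day 1: at least 1 day, because Visits 1 and 2 fall on different days, and at most 4 × 7 = 28 days.

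**Oldest image at Day 1 that triggers no new image under the table**

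Maximum age = days in 3 months + days of screening.

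| Case | Maximum age at Day 1 | Excess over 84 days |
|---|---|---|
| Shortest | 89 + 1 = 90 days (12.9 weeks) | 6 days |
| Worst | 92 + 28 = 120 days (17.1 weeks) | 36 days |

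Section 6 also recommends a 2-day window around Baseline. Adding it would give 122 days, but the four-week cap on screening holds the figure at 120.

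**Which images fall in the gap**

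The texts conflict when age at Screening plus days of screening exceeds 84, while the age at Screening is still within 3 months.

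- 14 days of screening: 84 − 14 = 70, so images from 71 days to 3 months old at Screening.
- 28 days of screening: 84 − 28 = 56, so images from 57 days to 3 months old at Screening.

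**One patient, side by side** (illustrative dates): image taken 80 days before Screening, Day 1 14 days later, so 80 + 14 = 94 days old at Day 1.

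- Table 6-1 comment: 80 days is within 3 months of Screening, so no new image is called for.
- Section 6 text: 94 days is outside 12 weeks of Day 1, so an X-ray should be done.
- Criterion 18: the image is outside its window.

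Two parts of Section 6 therefore give opposite instructions for the same patient, without extreme dates.

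**After alignment**: with 12 weeks before Baseline in the table, the limit is 84 days throughout and the excess is 0.

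**The case against.** The strongest reply is that harm requires a site to read one table cell in isolation. The Section 6 sentence about the projected Day 1 follows the rescreening text, but it speaks of patients generally and can be read as covering everyone. Section 6.2.5.1 makes an X-ray mandatory where none is in its window. Table 6-1 itself schedules the eligibility check at both Screening and Baseline. Section 6 requires all information relevant to Visit 2 to be available before treatment. Section 8.1 requires full verification of adherence to the eligibility criteria. Criteria 16, 17 and 20 and the tuberculosis assay at Screening cover part of the same risk. Moreover, the comment never states that an older image is acceptable. It says only when a new one is needed, and 120 days needs an image on the last permitted day, the longest three-month span and a full four weeks of screening.

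Most of this stands, and it is why the point is minor. It does not remove the contradiction. Monitoring detects an error after the fact, and monitors also need one rule to check against. The acceptance is by implication, but a schedule that says when imaging is needed also tells staff when it is not. The worst case is rare by construction, yet the 94-day example shows that ordinary dates are enough.

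**Conclusion.** The point holds for the Table 6-1 comment. It allows, by implication, an image 6 to 36 days older at Day 1 than criterion 18's window. These are differences between maximum permitted ages, not typical ages. They assume that 3 months means calendar months and that screening runs from 1 to 28 days. The documents give no basis for counting the patients affected. Sample size, power, alpha and the primary analysis are untouched.

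A reader might infer three stronger points that the documents do not support.

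- *That Section 6.2.5.1 opens a second long window, because* enrollment *means consent.* The glossary does describe enrollment as "Point/time of patient entry into the study at which informed consent must be obtained". But 6.2.5.1 tells sites to obtain a missing image once the other criteria look satisfied, which is after consent. Under the consent reading that image could never precede enrollment, yet it is meant to decide eligibility. Section 4 says "around 1580 patients will be enrolled at Baseline", and Sections 6.2.7 and 6.5.5 place enrollment after screening results. For the tuberculosis work-up, the Figure 6-1 footnote uses enrollment where the 6.2.7 text uses Baseline. The better reading is Baseline, which gives 84 days and no conflict.
- *That Section 6.2.5.1 admits patients treated after an abnormal image.* It says that untreated patients are ineligible. It does not say that treated patients are eligible. Section 4.2 excludes anyone who meets any criterion, so criterion 18 still applies to them.
- *That patients will in fact be dosed on outdated images.* The documents show a contradictory instruction and several checks against it. They do not show an outcome.

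**What to change.** In the Table 6-1 chest X-ray comment, replace the 3-month look-back from Screening with 12 weeks before Baseline (Day 1). For consistency, write Baseline instead of *enrollment* in both places in Section 6.2.5.1, where the context already points to it. Criterion 18 and Sections 5.5.1 and 6 need no change.

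Both are wording edits that can go into the next amendment. The cost is that a few patients need a newer image, with the added radiation where it is an X-ray or CT. The Section 6 text, read as covering all patients, already calls for those images.
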